## **Study Population**

This prospective study was approved by the Eskisehir Osmangazi University Faculty of Medicine institutional review board. Informed written consent was obtained from all participants prior to randomization. The participants were informed about procedures and side effects. The study protocol conformed to the ethical guidelines of the 1975 Declaration of Helsinki as revised in 2000 (the protocol number E.27336). From April 2019 to April 2020, 32 patients with chronic migraine were recruited sequentially at the Headache Unit of the XXXXX University. The selection of patients to treatment was made by randomization with a computer random number generator.

### **Inclusion and exclusion criteria were as follows:**

#### **Inclusion Criteria**

- Age 18–65;
- ICHD-3 defined chronic migraine 

#### **Exclusion Criteria**

- Patients who had been started on an effective preventive medication within the past three months;
- Medication-overuse headache;
- Treatment with peripheral nerve blocks, trigger point injections or botulinum toxin injections within the past three months;
- Known allergic reaction to local anaesthetics;
- Pregnancy or nursing;
- History of another headaches;
- History of chronic medical conditions (e.g. cardiovascular, hepatic, renal, endocrine);
- History of other chronic pain syndromes (e.g. low back pain and fibromyalgia).

The clinical data were collected from the headache diary. All participants were asked to record the number of the attack, severity of pain and analgesics consumption in this headache diary. A blind researcher made evaluation of these before the start of treatment and throughout the study. A visual analogue scale (VAS) from 0 (no pain) to 10 (intense pain) was used for the assessment of the pain intensity.

The study consisted of 2 groups: GON block (group GONB) and GON block + pulsed RF (group GONB+PRF). Each group had 16 patients.

### **Intervention**

In the operating room, an electrocardiogram, noninvasive blood pressure, and percutaneous oxygen saturation were monitored routinely for all patients. Patients were placed in the prone position. Ultrasound-guided GONB was performed to locate the nerve more accurately for all patients (Figure 1). All procedures were performed using a hockey stick probe. With 0.5 Hz sensorial stimulation, a 5-cm-long radiofrequency needle with a 0.5 cm active tip was advanced under ultrasound guidance in both pulsed PRF and nerve block groups. USG probe was located to medial one-third of the superior nuchal line between the occipital tubercle and mastoid process under sterile conditions. Finally, the placement of the needle was verified by Doppler imaging of the occipital artery. A 0.3-0.5 Hz sensory stimulus was given with the RF device, and the paresthesia sensation in the patient's occipital nerve dermatome was questioned, and location verification was performed. Then, GON block was performed in all patients by administering 5mg bupivacaine through a PRF needle. After the GON block, the PRF neuromodulation was applied at 42 degrees for 4 minutes in the GONB-PRF group. In the GONB group, the PRF generator was set for 4 minutes, and the time was waited, but no pulse was given.

## **Follow up**

The patients were examined for follow-ups at the 1st, 2nd, 3rd, and 6th months after the procedure. The severity and the number of migraine attacks, and the number of analgesic drugs were noted. The procedure's name performed on the patient was not written in the follow-up files. The blindness was broken after the study period was terminated, and the procedures were added to patients' files.

## **Statistical Analysis**

The SPSS Statistics for Windows, version 22.0 (SPSS Inc., Chicago, Ill., USA) was used as the statistical analysis program. Descriptive statistics (mean, standard deviation, frequency, and percentage) were used for the demographic and clinical characteristics. Histograms and the Shapiro-Wilk tests of normality were used to assess the normal distribution of means. The student's t-test was used for comparing two groups of continuous data, which are both normally distributed. Comparison of the VAS scores, number of headache attacks and analgesics before and after treatment was analyzed by Repeated Measures Analysis of Variance (ANOVA). For the Analysis of Variance, Greenhouse-Geisser F statistics were used in cases where the sphericity assumption was not met. A p-value of  $p < 0.05$  was statistically significant.

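### No between-arm contrast is set to decide whether pulsed RF adds to the block; the outcomes are tied by name only to a before/after ANOVA

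*Combined protocol and SAP*

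**What the plan says.** Allocation is random (Study Population): "The selection of patients to treatment was made by randomization with a computer random number generator". The group description, at the end of Exclusion Criteria, reads "The study consisted of 2 groups: GON block (group GONB) and GON block + pulsed RF (group GONB+PRF", with 16 patients in each.

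Under Intervention, the block is common to everyone: "Then, GON block was performed in all patients by administering 5mg bupivacaine through a PRF needle". The control arm gets a timed wait: "In the GONB group, the PRF generator was set for 4 minutes, and the time was waited, but no pulse was given". The arms therefore differ only in the pulse.

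Under Follow up, "The patients were examined for follow-ups at the 1st, 2nd, 3rd, and 6th months after the procedure", and "The severity and the number of migraine attacks, and the number of analgesic drugs were noted". The diary is also evaluated before treatment, so each outcome has five occasions.

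The Statistical Analysis section gives two inferential methods:

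- For the three outcomes: "Comparison of the VAS scores, number of headache attacks and analgesics before and after treatment was analyzed by Repeated Measures Analysis of Variance (ANOVA". The Greenhouse-Geisser correction is to be used where sphericity fails.
- A Student's t-test for two groups of normally distributed continuous data, with no outcome, visit or scale (value or change) attached.

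The text available contains no statement of objective, primary outcome or deciding visit. One part of the document was removed before review, so I draw nothing from the missing objective. The question is inferred from the design.

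**The concern.** A trial in which everyone receives the block can isolate the effect of the pulse only by comparing the arms. The one comparison that the plan attaches to VAS, attacks and analgesics is before against after. Taken literally, that is the visit line of the ANOVA. It measures how far all patients improved, including any response to the block, placebo response and regression to the mean. It would be significant if both arms improved equally.

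A between-arm comparison is possible under the plan, as an ANOVA group line, a group-by-visit line or a t-test at some visit. These answer different questions, and none is named as deciding. If the choice is made once results are visible, the reported p-value no longer has a 5% error rate. With 16 per arm and modest power, which line is chosen can easily settle the conclusion.

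**Working it through.** The documents give no SD, effect size, correlation or power figure, so there is no design figure to reproduce. 16 + 16 = 32 agrees with the stated total.

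**Inputs from the documents:** 16 per arm; baseline plus months 1, 2, 3 and 6; significance at p<0.05.

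**Assumed inputs:** two-sided tests; normal data; equal correlation ρ of 0.3, 0.5 or 0.7 between any two occasions; no dropout. Percentages separated by slashes follow that order of ρ. Simulations used 20,000 to 40,000 runs per setting.

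**Step 1. What each line does with no pulsed RF effect and a shared 0.5 SD improvement.**

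| Line | Significant at p<0.05 |
|---|---|
| Visit (before/after) | 65/81/97% |
| Group | about 5% |
| Group-by-visit | about 5% |
| Baseline-adjusted between-arm contrast (month 6, or follow-up average) | about 5% |

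Each between-arm line is valid alone. The visit-line rate only shows that a shared improvement is detectable. It becomes an error rate only if that line is misread as evidence for pulsed RF.

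**Step 2. Choosing the between-arm line after seeing results, one outcome.**

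- Narrow reading: the ANOVA includes group and the t-tests serve baseline data only. Two lines remain, group and group-by-visit. Under the assumed correlation structure they are close to independent, so 1 − 0.95² = 1 − 0.9025 = 9.75%. Simulation gives about 9-10%.
- Broad reading: t-tests at the four follow-up visits are added, giving 2 + 4 = 6 candidates. They are correlated, so simulation is needed. It gives about 20-21/19/17%, or 16-21% across repeat runs.
- One contrast named in advance: 5%.

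These figures cover one outcome. Three are recorded and none is named primary in the text available, so the room for choice is wider than they show.

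**Step 3. What baseline adjustment gains at one visit, true difference d = 0.8 SD.**

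- t-test at that visit: noncentrality d√(n/2) = 0.8 × √8 = 2.26 on 30 degrees of freedom; power 59%.
- ANCOVA on baseline: residual variance is multiplied by about 1 − ρ², so noncentrality is about 2.26/√(1 − ρ²) = 2.37/2.61/3.17. Simulated power is about 61/70/85%.

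**Step 4. Averaging against a single visit, using ANCOVA.**

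- Constant 0.8 SD effect over follow-up: the adjusted average has 93-98% power. The group line has 52-75% and group-by-visit 44-84%.
- 0.8 SD effect at month 6 only: the adjusted average has 14-17%. The adjusted month-6 contrast has 61-85% and group-by-visit 44-84%.

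Neither choice is best for every shape of effect.

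**The case against.** The strongest reply is that a repeated-measures ANOVA in a two-arm, five-occasion trial ordinarily carries group and group-by-visit terms, and that the plan does mention a two-group test. That is fair. A reader might infer that the between-arm comparison is omitted; the documents do not support this, because a group term is not ruled out. What stands is that even on this reading two between-arm lines remain with neither named as deciding, which is why the range starts at about 9-10% and not at 16-21%.

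A reader might also infer that the trial carries a 65-97% false-positive rate. It does not. That rate applies only if the visit line is read as efficacy, and nothing in the document says it will be.

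A third tempting reading is that ANOVAs run separately by arm would produce significance in the pulsed RF arm alone. The plan describes no such use. The rate also depends heavily on the shared improvement: with no pulsed RF effect it is 22/25/21% at 0.5 SD, 7/1/0% at 1.0 SD and 0% at 1.5 SD, so roughly 0-25%. It adds nothing to the case.

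Finally, ANCOVA could be called a preference, since the group and group-by-visit lines already hold 5%. That is correct as to validity: the minimum repair is to name one between-arm line for one outcome. Baseline adjustment is recommended for its power, on data already collected.

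**Conclusion.** The point holds and needs correcting before any efficacy claim is made. The plan ties its outcomes by name to a comparison that cannot show what pulsed RF adds, and sets no between-arm contrast to decide that question. Choosing among the between-arm lines for one outcome after seeing results raises the chance of at least one p<0.05 from 5% to about 9-10% on the narrow reading and 16-21% on the broad one. These sizes rest on normal data, correlation 0.3 to 0.7, no dropout and 16 per arm.

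The finding concerns what is specified. It does not show that group was left out of the analysis that was run, or that a line was in fact picked after the event.

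**What to change.** State in the Statistical Analysis section that the efficacy conclusion rests on the GONB+PRF versus GONB difference for one named outcome. Take it at one named visit or averaged over months 1, 2, 3 and 6; that choice is the sponsor's. Estimate it by ANCOVA with the baseline value as covariate, and report the difference with its 95% CI and p-value. Treat other outcomes, visits and ANOVA lines as secondary, and within-arm before/after changes as descriptive.

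The cost is wording and a different SPSS command, with no new patients or measurements. There are three downsides: before/after p-values can no longer support pulsed RF efficacy, the remaining between-arm lines no longer decide, and averaging loses power if the effect appears at one visit only.

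There is a limit on what the repair can achieve. Follow up reports that "The blindness was broken after the study period was terminated". If data by arm have already been seen, the contrast and the choice of primary outcome must be labelled post hoc. Naming them now makes the report transparent, but does not restore the 5% error rate of a contrast fixed in advance.

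### No between-group comparison is described with baseline as a covariate, so with 16 patients per arm the group difference at a visit may be estimated less precisely than the collected data allow

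*Combined protocol and SAP*

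**What the plan says.** All points are in the combined protocol and SAP.

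- **Baseline exists for every outcome.** The text after the Exclusion Criteria list describes diary records of attacks, pain severity and analgesic use, and adds: "A blind researcher made evaluation of these before the start of treatment and throughout the study".
- **Follow-up.** The Follow up section states: "The patients were examined for follow-ups at the 1st, 2nd, 3rd, and 6th months after the procedure". The same three outcomes are collected there: "The severity and the number of migraine attacks, and the number of analgesic drugs were noted".
- **Size.** "Each group had 16 patients".
- **Analysis.** The Statistical Analysis section names two inferential methods. One is general: "The student's t-test was used for comparing two groups of continuous data, which are both normally distributed". It specifies neither outcome nor visit. The other is tied to the three outcomes: "Comparison of the VAS scores, number of headache attacks and analgesics before and after treatment was analyzed by Repeated Measures Analysis of Variance (ANOVA". For that ANOVA, "Greenhouse-Geisser F statistics were used in cases where the sphericity assumption was not met". No group term, group-by-time term or covariate is stated, and no effect size, SD, correlation or power is given.

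**The concern.** The plan leaves three readings of how the arms are compared, and none uses the baseline value as a regression covariate.

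1. A t-test at a follow-up visit ignores baseline.
2. A group main effect from the before/after ANOVA averages in the pre-treatment visit, where no treatment effect can exist. A constant effect over four follow-ups shrinks to 4/5 of its size.
3. A group-by-time contrast does use baseline, but as a change score, which fixes the slope on baseline at 1.

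With only 32 patients, imprecision is the main risk to a useful answer, and the baseline data are already in hand. A chance baseline gap is also not rare: the probability that the arms differ by more than 0.5 SD on a given outcome is 2 × (1 − Φ(0.5/√(2/16))) = 0.157. A follow-up-only comparison carries rho times that gap into its estimate.

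**Working it through.** **Inputs.** From the documents: 16 per arm (N = 32), one pre-treatment and four post-treatment assessments, significance at 0.05. Assumed: two-sided test, normal data, equal variances (SD = 1), no dropout, and rho over a range. The plan has no figure of its own to reproduce.

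**Variance of the group difference at one visit**

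- Follow-up-only t-test: 2/16 = 0.125.
- Change score, each visit on its own 30 df: 2(1 − rho) × 2/16.
- ANCOVA: (1 − rho²) × (1 + 1/28) × 2/16, where 1 + 1/(N − 4) = 29/28 = 1.036 is the cost of estimating the slope.

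Critical values are 2.042 (30 df) for the first two and 2.045 (29 df) for ANCOVA. The width ratio is the square root of the variance ratio × 2.045/2.042.

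| rho | ANCOVA / t-test variance | CI width change | ANCOVA / change-score variance | CI width change |
|---|---|---|---|---|
| 0 | 1.036 | 2% wider | 0.518 | 28% narrower |
| 0.2 | 0.994 | none | 0.621 | 21% narrower |
| 0.3 | 0.943 | 3% narrower | 0.673 | 18% narrower |
| 0.5 | 0.777 | 12% narrower | 0.777 | 12% narrower |
| 0.7 | 0.528 | 27% narrower | 0.880 | 6% narrower |

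Example at rho 0.5: (1 − 0.25) × 1.036 = 0.777; √0.777 × 2.045/2.042 = 0.883. In SD units, mean interval widths at rho 0.3/0.5/0.7 are 1.43 throughout (t-test), 1.69/1.43/1.11 (change score) and 1.39/1.26/1.04 (ANCOVA). Simulation agreed with these.

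**Break-even**

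- Against the t-test: (1 − rho²) × 29/28 = 1 gives rho² = 1/29, so rho = 0.186 on variance, and 0.193 on interval width.
- Against the change score: (1 + rho)/2 × 29/28 = 1 gives rho = 56/29 − 1 = 0.931. ANCOVA is better below this, and its advantage is largest at low rho.

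**If the correlation decays.** Suppose correlation is rho to the power √(months apart). A one-month value of 0.5 becomes 0.5^2.449 = 0.18 at month 6, so there is no gain over the t-test. A value of 0.7 becomes 0.42, and the narrowing is about 7%, not 27%.

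**Counts.** Attacks and analgesics were simulated as negative binomial (assumed means 20 before and 12 after, 30% fewer in one arm, one visit). At latent rho 0.2/0.3/0.5/0.7, power was 46–47% for the t-test against 47/49/56/72% for ANCOVA with a coefficient of variation of 0.4. With 0.7 it was 22–23% against 22/24/28/37%. The pattern is the same as for normal data.

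**Power against the omnibus group-by-time test** (assumed effects in SD at months 1/2/3/6, compound symmetry, rho 0.2/0.3/0.5/0.7)

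| Effect | Group-by-time | ANCOVA, four-visit mean | Baseline-adjusted joint test |
|---|---|---|---|
| 0.8/0.8/0.8/0.8 | 39/45/60/84% | 94/94/94/98% | 78/76/76/88% |
| 0.8/0.6/0.4/0 | 39/45/60/84% | 52/49/51/62% | 51/52/61/80% |

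ANCOVA at month 1 alone, if named in advance, gives 59/62/71/85% in the fading case. Which analysis has more power therefore depends on the effect pattern and the contrast.

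**The case against.** Four objections have weight.

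- **The t-test figures rest on an unstated reading.** The plan assigns only the ANOVA to the three outcomes. The t-test sentence is general and could concern baseline characteristics. This stands: the 3, 12 and 27% apply only if the t-test covers outcomes at follow-up.
- **The ANOVA already uses baseline.** True on the group-by-time reading, so a reader should not infer that the plan discards it. But that reading is not settled by the Greenhouse-Geisser sentence, which would fit a plain time effect within each arm equally well. Even if it is right, fixing the slope at 1 costs precision at a visit unless rho is above about 0.93.
- **The size depends on an unknown rho.** This also stands. A reader might infer one cut-off, such as 0.3, above which precision is lost. The documents give no such figure and the arithmetic does not produce one: break-even is about 0.19 against a t-test, and the pattern reverses against a change score.
- **It is late.** The plan is written in the past tense, and the Follow up section says: "The blindness was broken after the study period was terminated". An analysis added after unblinding cannot recover prespecified precision. If the visit is then chosen freely, the chance under no effect that at least one of four per-visit ANCOVAs is significant is 17–18% per outcome.

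Two stronger readings are not supported. One is that the planned tests are biased or invalid: the documents describe computer-generated random allocation, and randomisation keeps the tests valid without adjustment. The other is that ANCOVA always has more power: with a fading effect at rho 0.7, the omnibus test has 84% against 62% for ANCOVA on the mean.

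**Conclusion.** The point holds as one of precision and is worth considering rather than essential. The Statistical Analysis section describes no baseline-adjusted between-group comparison, although the data for it exist. ANCOVA would sharpen the group difference at a visit against a follow-up-only t-test if rho exceeds about 0.2, with negligible gain up to about 0.3 and less gain at later visits if correlation decays. It would also sharpen it against a change-type contrast at almost any plausible rho. These sizes rest on normality, equal variances, no dropout and assumed correlations. No claim is made about which analysis would reach significance.

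**What to change.** For each outcome, specify the between-group comparison as ANCOVA, or one mixed model, on post-treatment values only. Use that outcome's own baseline as covariate and group as a fixed effect; in the mixed model add visit and group-by-visit. In the same sentence name one contrast: a single visit, the four-visit mean, or the joint test over visits. If the effect may fade, a named visit or the joint test is safer than the mean. Report adjusted differences with 95% confidence intervals, and check residuals for the two count outcomes. If the data are already unblinded, label this analysis post hoc and report the planned ANOVA, with its group term stated, alongside it.

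The cost is SAP wording and a few lines of SPSS syntax on data already collected. Statistically it is one degree of freedom plus the estimated slope: an interval about 2% wider if rho is 0. There is also a possible loss of power against group-by-time if the effect fades, rho is high and the four-visit mean is chosen.

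### Neither named group analysis uses the baseline value as a covariate, and the repeated-measures ANOVA keeps only patients with complete values; with 16 per group this gives up precision that a baseline-adjusted mixed model would probably recover.

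*Combined protocol and SAP*

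**What the plan says.** The Statistical Analysis section covers three outcomes in one sentence: "Comparison of the VAS scores, number of headache attacks and analgesics before and after treatment" was "analyzed by Repeated Measures Analysis of Variance (ANOVA", in SPSS 22, with Greenhouse-Geisser F statistics where sphericity fails. That correction points to the classical univariate procedure. The same section assigns Student's t-test to two-group comparisons of normally distributed continuous data, without saying which outcome or visit. It names no baseline covariate, group-by-time term, analysis set or rule for missing values.

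The number of values per patient has to be pieced together:

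- Baseline (text under Exclusion Criteria): "A blind researcher made evaluation of these before the start of treatment and throughout the study".
- Follow-up (Follow up section): "The patients were examined for follow-ups at the 1st, 2nd, 3rd, and 6th months after the procedure".

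That makes five values per outcome: one before treatment and four after.

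The source is a diary ("The clinical data were collected from the headache diary"), and the size is stated as "Each group had 16 patients". On timing, the Follow up section says "The blindness was broken after the study period was terminated".

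**The concern.** Two features of the named analyses cost precision, and a trial of 32 patients has little to spare.

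The first does not depend on missing data. Baseline is measured, but it appears to enter only as one level of the time factor. It does not enter the t-test at all. Using it as a covariate removes the part of the post-treatment variation that it predicts.

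The second is conditional. The classical repeated-measures ANOVA needs every repeated value, so a patient with four of five values is dropped from that outcome entirely.

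The section also leaves open which test answers the treatment question. The ANOVA sentence speaks of before and after and mentions no groups, while the only explicit two-group test is the t-test. The cost therefore has to be worked out for both.

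**Working it through.** **Inputs from the document.** 16 patients per group (text under Exclusion Criteria); one baseline and four follow-up values (text under Exclusion Criteria; Follow up). The document gives no effect size, SD, power or dropout rate, so there is no precision figure of its own to reproduce. Only 16 + 16 = 32 can be checked, and it agrees.

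**Assumptions.** SD σ = 2 VAS points; the same correlation ρ between any two time points, at 0.4, 0.6 and 0.8; approximately normal data.

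**Formulas.** Each variance is a factor v times 2σ²/n = 2 × 4/16 = 0.5, so SE = √(0.5v).

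- Change contrast (mean of four follow-ups minus baseline, which lies inside a group-by-time term): v = (1+3ρ)/4 + 1 − 2ρ = 5(1−ρ)/4.
- Same mean, baseline-adjusted: v = k[(1+3ρ)/4 − ρ²] = k(1−ρ)(1+4ρ)/4, where k = 1 + 1/(32−4) = 1.036 is the cost of estimating the slope.
- Single-visit t-test: v = 1.
- Single visit, baseline-adjusted: v = k(1−ρ²).

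At ρ = 0.6:

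- Change: v = 5 × 0.4/4 = 0.50, SE = √0.25 = 0.50.
- Adjusted mean: v = 1.036 × 0.4 × 3.4/4 = 0.352, SE = √0.176 = 0.42.
- t-test: SE = √0.5 = 0.71.
- Adjusted single visit: v = 1.036 × 0.64 = 0.663, SE = √0.331 = 0.58.

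| SE of the group difference (VAS points) | ρ = 0.4 | ρ = 0.6 | ρ = 0.8 |
|---|---|---|---|
| Four-visit mean, ANOVA change contrast | 0.61 | 0.50 | 0.35 |
| Four-visit mean, baseline-adjusted | 0.45 | 0.42 | 0.33 |
| Single visit, t-test | 0.71 | 0.71 | 0.71 |
| Single visit, baseline-adjusted | 0.66 | 0.58 | 0.43 |

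For the four-visit mean at ρ = 0.6, the variance ratio is 0.352/0.50 = 0.70. The change contrast would need about 16/0.704 = 22.7, so 23 patients per group, to match the adjusted analysis of 16.

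**Where the gain ends.** Against the change contrast, k(1+4ρ)/5 = 1 at ρ = (5/k − 1)/4 = 0.96. Against the single-visit t-test, k(1−ρ²) = 1 at ρ = √(1 − 1/k) = 0.19. At ρ = 0, adjustment costs about 4% in variance.

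**If values were missing.** Suppose a fraction p is missing independently at each of the four follow-ups. Patients left in the ANOVA are 32(1−p)⁴:

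- p = 5%: 32 × 0.8145 = 26.1.
- p = 10%: 32 × 0.6561 = 21.0.

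If missing values cluster within patients (beta-binomial, assumed intraclass correlation 0.5), 28.8 and 25.8 remain.

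The SE grows roughly as one over the square root of the fraction kept. At ρ = 0.6 and p = 5%, 0.50 × 1/√0.8145 = 0.55; at 10%, 0.50 × 1/√0.6561 = 0.62. Simulation (1,500 data sets, covariance treated as known) gave 0.56 and 0.63, against 0.50 and 0.51 for the same contrast on all observed values.

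**Checking a fallback covariance.** Null simulations used equal correlation 0.6, complete data, 16 per group and model-based standard errors. Two runs of 500 and 700 data sets (Monte Carlo error about 0.01) gave:

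- Spatial-power: SEs about 15–16% too small, type I error 0.09–0.10.
- First-order ante-dependence: SEs about 9–13% too small, type I error 0.05–0.08.

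**The case against.** The strongest reply is that nothing in the plan is invalid. With complete data, a Greenhouse-Geisser ANOVA is a legitimate analysis and baseline is in it as a time level. What remains is efficiency, and the size of the gain rests on an SD and correlations that the document does not give. This stands, and it limits the point to precision.

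A reader might infer three stronger things that the document does not support:

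- **That patients were dropped.** The document neither reports missing values nor says that there were none. Because the data come from a diary, a missed visit need not lose a value. Whether deletion would also bias the comparison depends on why values are missing, which cannot be judged here.
- **That omitting baseline always costs precision.** It does not. There is no gain over a single-visit t-test below correlation about 0.19, or over the change contrast above about 0.96. At 0.8 the gain over the change contrast is only about 7% in SE.
- **That the mixed model itself brings the gain.** With complete data the gain comes from the covariate. The mixed model adds the use of incomplete patients.

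Two of the three outcomes are counts, so the normal-theory figures are only approximate for them. Timing also counts against replacing the analysis: the document is written in the past tense and describes unblinding after the study period, so a change is probably post hoc.

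**Conclusion.** The point holds as one about precision, not validity. Under the assumed equal correlation of 0.4 to 0.8, baseline adjustment lowers the SE of the four-visit mean difference by about 27%, 16% and 7% against the ANOVA change contrast. Against a single-visit t-test the reductions are about 7%, 19% and 39%. The percentages do not depend on the assumed SD; the SEs in VAS points do.

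Listwise deletion is a second, conditional cost. It would remove about 6 or 11 of 32 patients at 5% or 10% independent missingness, fewer with clustering, and none if the data are complete. The change is worth making because it is cheap, but the planned ANOVA does not have to be discarded.

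**What to change.** Compare the randomised groups, for each outcome, with a linear mixed model (REML) on all observed post-treatment values. Use fixed effects for group, visit, group-by-visit and baseline, an unstructured covariance and Satterthwaite degrees of freedom.

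- **Contrast.** Name one, for example the mean group difference over months 1, 2, 3 and 6, with per-visit differences as secondary.
- **Fallback.** If the unstructured fit does not converge, use a simpler covariance only with a small-sample-corrected robust standard error, or use ANCOVA of each patient's mean post-treatment value on baseline. Do not rely on model-based standard errors from spatial-power or ante-dependence structures, which are too small under equal correlation.
- **Counts.** Check residuals and treat any count model as a sensitivity analysis. Unweighted GEE generally needs values missing completely at random, a stronger assumption than the mixed model's missing at random.
- **Reporting.** Give numbers analysed per arm, outcome and visit, and state the missing-data assumption. If the data are already unblinded, label this analysis post hoc and show it beside the planned ANOVA.

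The cost is SAP or report wording and a different SPSS procedure; no new data are needed. The downside is that a covariance structure must be chosen, and convergence is less certain with 32 patients. The unstructured fit converged in all 1,500 simulated data sets with 5% missing, but real data may be less regular.
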